15.0 Study Schedule

Detailed schedules of all study visits and procedures are presented in Schedule of Visits and Procedures ([Table 2](#)).

Table 2: Schedule of Visits and Procedures (Study SCY-078-304)

Study Week/Day	Screen ^a	Acute Phase (Days -14 to -1 [+3 d])			Prevention of Recurrence								Unsch ^c	
		D-14 ^a	D-11 & -8 Phone	D-4 to -2 Lab	W1/ D1 (BL)	W4/ D28 (±3 d)	W8/ D56 (±3 d)	W12/ D84 (±3 d)	W16/D112 Phone ^b	W20/D140 Phone ^b	W24/ D168 (TOC) (±3 d)	W28 & W32 Phone ^b	W36 (EOFU) (±3 d)	
Study Week/Day	D -16 to -14	D-14 ^a	D-11 & -8 Phone	D-4 to -2 Lab	W1/ D1 (BL)	W4/ D28 (±3 d)	W8/ D56 (±3 d)	W12/ D84 (±3 d)	W16/D112 Phone ^b	W20/D140 Phone ^b	W24/ D168 (TOC) (±3 d)	W28 & W32 Phone ^b	W36 (EOFU) (±3 d)	Unsch ^c
Informed Consent	X													
Assignment of Subject ID number	X													
Inclusion/exclusion criteria	X				X									
Medical history and demographics	X													
Abbreviated physical exam	X				X			X			X			If needed
Urine pregnancy test	X				X									If needed
Vulvovaginal sample for KOH ^d	X					If PR ^e	If PR ^e	If PR ^e			If PR ^e		If PR ^e	If PR ^e
Vulvovaginal sample for fungal culture ^d	X				X	If PR ^e	If PR ^e	X			X		X	If PR ^e
Vulvovaginal sample for pH ^d	X				X	If PR ^e	If PR ^e	If PR ^e			If PR ^e		If PR ^e	If PR ^e
Vulvovaginal sample for other pathogens ^d	X					If PR ^e	If PR ^e	If PR ^e			If PR ^e		If PR ^e	If PR ^e
Vulvovaginal exam ^f and rating of signs by the investigator	X				X	If PR ^e	If PR ^e	X			X		If PR ^e	If PR ^e
Rating of vulvovaginal symptoms by the subject ^g	X	X-----X			X -----X								X	
Open-label FLU dispensing		X												
Open-label FLU dosing ^h		X	X											
Subject diary dispensing and collection		X			X			X			X		X	

Study Week/Day	Screen ^a	Acute Phase (Days -14 to -1 [+3 d])			Prevention of Recurrence								Unsch ^c	
					Study Treatment Period (D1 to W24)						Follow-up Period (W25 to W36)			
Study Procedures	D -16 to -14	D-14 ^a	D -11 & -8 Phone	D -4 to -2 Lab	W1/ D1 (BL)	W4/ D28 (±3 d)	W8/ D56 (±3 d)	W12/ D84 (±3 d)	W16/D112 Phone ^b	W20/D140 Phone ^b	W24/ D168 (TOC) (±3 d)	W28 & W32 Phone ^b	W36 (EOFU) (±3 d)	
Subject diary completion		X-----										X		
Subject diary review					X	X	X	X				X		X
Sample collection for safety labs (hematology and blood chemistry)				X ⁱ				X						X ^j
Open-label FLU collection and compliance evaluation					X									
Assessment of clinical outcome to FLU treatment					X ^k									
Randomization					X									
Blinded study drug dispensing					X			X						
Blinded study drug dosing ^l					X	X	X	X	X	X				
Quality-of-life assessment ^m	X			X			X				X		X	
Assessment for potential recurrence					X	X	X	X	X	X	X	X	X	X
Blinded study drug compliance evaluation					X	X	X	X	X	X	X	X		
Blinded study drug collection								X				X		
Vital Signs	X	X			X	X	X	X			X		X	X
Prior & concomitant medication review	X	X	X		X	X	X	X	X	X	X	X	X	X
Adverse event monitoring	X	X	X		X	X	X	X	X	X	X	X	X	X

Abbreviations: BL = Baseline; d = day; D = Day; EOFU = end of follow-up; FLU = fluconazole; ID = identification; KOH = potassium hydroxide; Phone = Phone contact; PR = potential recurrence; Screen = Screening; TOC = test of cure; Unsch = unscheduled; VSS = vulvovaginal signs and symptoms; VVC = vulvovaginal candidiasis; W = Week;

Note regarding visits: Whenever possible, on-site visits and phone contacts will be scheduled to occur on the date of dosing (or as close to the date of dosing as possible) to facilitate reminding subjects to take their study doses. This is applicable for the Baseline (Day 1), Week 4, Week 8, Week 12, Week 16 (phone contact), and Week 20 (phone contact) visits. Phone contacts will be conducted to check for adverse events, treatment compliance, potential recurrence, and concomitant medication use, including other antifungal agents.

	Screen ^a	Acute Phase (Days -14 to -1 [+3 d])		Prevention of Recurrence									Unsch ^c	
				Study Treatment Period (D1 to W24)						Follow-up Period (W25 to W36)				
Study Week/Day	D -16 to -14	D-14 ^a	D -11 & -8 Phone	D -4 to -2 Lab	W1/ D1 (BL)	W4/ D28 (±3 d)	W8/ D56 (±3 d)	W12/ D84 (±3 d)	W16/D112 Phone ^b	W20/D140 Phone ^b	W24/ D168 (TOC) (±3 d)	W28 & W32 Phone ^b	W36 (EOFU) (±3 d)	
Study Procedures														
a.	Screening and Day-14 may occur on the same day.													
b.	If there is suspicion of a potential recurrence, subjects will be strongly discouraged from self-administering any treatment and will be instructed to visit the study center for a proper evaluation of their recurrence before initiating any VVC treatment.													
c.	Unscheduled visits should be conducted anytime that there are symptoms indicating a potential recurrence or an adverse event. If there is suspicion of a potential recurrence, subjects will be strongly discouraged from self-administering any treatment and will be instructed to visit the study center for a proper evaluation of their recurrence before initiating any VVC treatment.													
d.	Vulvovaginal specimens will be obtained at the specified visits and anytime that a recurrence is suspected for local vaginal pH determination and KOH testing as well as to rule out bacterial vaginosis and Trichomonas vaginalis (wet-mount or other, process locally). Testing for Neisseria Gonorrhoeae , Chlamydia trachomatis or Herpes virus may also be conducted if these pathogens are suspected (central laboratory). Samples for fungal culture should also be collected for processing at a central laboratory. Susceptibility testing will be done centrally at Screening and for all positive cultures during the study.													
e.	Only if there is suspicion of a potential recurrence.													
f.	If a subject is actively menstruating at an on-site study visit that requires a vaginal exam, the visit should be rescheduled as soon as the subject's period ends but in no case more than 7 days after the initially scheduled visit.													
g.	From Baseline (Day 1) through the Week 36 (EOFU) visit, subjects will rate their symptoms and record their scores on the VSS Scale included in their subject diaries. Symptoms of infection will be rated on a weekly basis and at the time of each scheduled or unscheduled visit to the site.													
h.	The first dose of fluconazole will be administered at the site on Day -14, after all other visit procedures have been done. The remaining doses will be self-administered by the subjects at home.													
i.	Conducted by the central lab. Results will be reviewed at Baseline (Day 1).													
j.	Only if needed to follow up on a lab abnormality													
k.	If the subject has a culture-confirmed Candida spp. infection from the sample collected at Screening, achieves a significant resolution of all signs and symptoms of infection (total composite score ≤ 2 on the VSS Scale) and meets other eligibility criteria for the study, she will enter the Prevention of Recurrence Phase. Subjects who fail treatment with open-label fluconazole in the Acute Phase but continue to meet all other eligibility criteria will enter the open-label ibrexafungerp Nested Sub-Study (see Section 21.3 [Appendix C]). Subjects who are not eligible for this study or the Nested Sub-Study will be discontinued.													
l.	Oral ibrexafungerp or placebo administered as a single-day treatment repeated every 4 weeks (28 days [± 3]) for a total of 6 single-day treatments (Baseline [Day 1], Week 4, Week 8, Week 12, Week 16 and Week 20). Each single-day treatment will consist of two doses of ibrexafungerp 300 mg each or placebo given 12 (± 4) hours apart. Subjects will continue study drug treatment regardless of recurrence and/or administration of antifungal therapy. The first dose will be administered at the study site (Baseline [Day 1]) and the remaining doses will be self-administered by the subjects at home. Study drug should be administered preferably with or													

	Screen ^a	Acute Phase (Days -14 to -1 [+3 d])			Prevention of Recurrence								Unsch ^c	
					Study Treatment Period (D1 to W24)						Follow-up Period (W25 to W36)			
Study Week/Day	D -16 to -14	D-14 ^a	D -11 & -8 Phone	D -4 to -2 Lab	W1/ D1 (BL)	W4/ D28 (±3 d)	W8/ D56 (±3 d)	W12/ D84 (±3 d)	W16/D112 Phone ^b	W20/D140 Phone ^b	W24/ D168 (TOC) (±3 d)	W28 & W32 Phone ^b	W36 (EOFU) (±3 d)	
Study Procedures														

immediately after a meal.

m. Quality of Life tools will include: Euro Quol 5 Dimensions (EQ-5D), Short Form Health Survey (SF-36) and Female Sexual Distress-Revised Scale (FSDS)

16.0 Safety Assessments and Monitoring

16.1 Definition of an Adverse Event

An AE is any untoward medical occurrence associated with the use of a drug in humans, whether or not considered drug related. An AE can therefore be any unfavorable and unintended sign (including an abnormal laboratory finding), symptom or disease temporally associated with the use of a study drug/study intervention, whether or not related to the study drug/study intervention.

Any laboratory abnormality that is deemed to be clinically significant in the opinion of the investigator will be considered an AE and should be recorded in the eCRF, whether or not it is related to the study drug.

Stable chronic conditions that are present prior to clinical trial enrollment and do not worsen are not considered AEs and will be accounted for in the subject's medical history.

The following can be considered AEs:

- An exacerbation of a pre-existing illness
- An increase in frequency or intensity of a pre-existing episodic event or condition
- A condition detected or diagnosed after the initiation of treatment with study medication, even though it may have been present prior to the start of the study
- Continuous persistent disease or symptoms present at Baseline (Day 1) that worsen after signing the informed consent or following the initiation of treatment with study medication

The following are **not** considered AEs:

- Medical or surgical procedures (e.g., surgery, endoscopy, tooth extraction or transfusion); the condition that leads to the procedure is an AE
- Pre-existing disease or conditions present or detected at the start of the study that do not worsen
- Situations where an untoward medical occurrence has not occurred (e.g., hospitalizations for cosmetic surgery or elective surgery or social/convenience admissions)
- The disease being studied, or signs or symptoms associated with the disease, unless more severe than expected for the subject's condition or a worsening of the disease being studied

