14.18.2 Procedures for Potential Recurrences

Potential recurrences will be assessed based on clinical and mycological outcomes and need for other antifungal treatment. If a subject has symptoms suggestive of *Candida* infection (itching, burning, irritation) that in the opinion of the investigator may require antifungal therapy, the following procedures must be completed:

- Rate and document symptoms in the eCRF ([Section 14.9](#)),
- Perform vaginal examination to rate signs and document in the eCRF ([Section 14.8](#)),
- Measure vaginal pH at the site and document results in the eCRF ([Section 14.7](#)),
- Collect vaginal sample for KOH testing and investigation of potential bacterial vaginosis and *Trichomonas vaginalis* infection at the site or by the local laboratory ([Section 14.7](#)),
- Collect vaginal samples for fungal culture by the central laboratory ([Section 14.7](#)), and
- Document any additional antifungal treatment used by the subjects ([Section 14.21](#)).

All of the procedures above should be completed prior to administration of rescue antifungal medication. **Subjects participating in the study should be strongly discouraged from self-administering any treatment for a potential recurrence.** Ideally, if the severity of the symptoms allows based on the investigator's judgment, the initiation of antifungal therapy should be delayed until results from the vaginal culture are available to confirm that the episode is due to *Candida* spp. and not to other cause of vaginitis.

The following steps should be followed for potential recurrences:

- If the vaginal culture results are positive for yeast and the subject remains symptomatic (VSS score ≥ 3), rescue antifungal therapy should be offered and the episode should be listed as a Mycologically Proven Recurrence. Rescue antifungal therapy should be documented in the eCRF.
- If the vaginal culture results are negative for yeast, other causes of vaginitis (e.g. bacterial vaginitis or trichomoniasis) should be further investigated and rescue antifungal therapy may not be indicated. Subjects with a diagnosis of vaginitis caused by pathogens other than yeast (e.g. bacterial vaginitis or trichomoniasis) may receive treatment for these conditions as indicated and the vaginitis episode should be listed as AE.

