14.22 Adverse Event Monitoring

AEs will be recorded and reviewed at all scheduled and unscheduled study visits from the time the ICF is signed (Screening) through Week 24 (TOC). New AEs starting after Week 24 and until Week 36 will be recorded only if they led to the use of other antifungal medications or topical vaginal treatment, if they are a vaginal bacterial or parasitic infection, or if they are deemed related to the previously administered study drug. See [Section 16.0](#) for further reference.

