18.0 Analytical Plan

All statistical analysis will be performed using SAS® version 9.3 or later, unless otherwise stated. All statistical tests will be two-sided and interpreted at a 5% significance level.

Descriptive statistics (i.e., mean, standard deviation, median, minimum, maximum, etc.) will be provided for all continuous variables; frequencies and percentages will be tabulated for incidence and categorical variables. For parameters measured over time, observed values and changes from baseline will be described for each time point.

The Mycologically Proven Recurrence and Mycological Eradication rates will be described by baseline *Candida* species, when the number of isolates per species allows.

The percentage of subjects with Mycologically Proven Recurrence will be described by number of VVC episodes in the 12 months prior to randomization.

All analyses will be presented by treatment group, as appropriate. Unless otherwise stated, data will be analyzed as is with no imputation. No adjustment for multiplicity will be employed.

A Statistical Analysis Plan (SAP) describing all final statistical analyses in detail will be provided as a separate document. The SAP will be finalized prior to the unblinding of the study treatments for analysis.

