18.1 Sample Size Determination

The primary endpoint of the study is the percentage of subjects with documented Clinical Success up to TOC (Week 24). Assuming response rates of 65% and 43% for ibrexafungerp and placebo, respectively; 90% power; and an alpha level of 0.05, approximately 240 subjects randomized at a 1:1 ratio are needed to declare a difference between ibrexafungerp and placebo at Week 24 based on Fisher's Exact test.

In order to be randomized, a subject should have achieved the proposed significant resolution of signs and symptoms (total composite score ≤ 2 on the VSS Scale) after receiving fluconazole therapy for an acute episode and have a positive culture for *Candida* spp. from the sample collected at Screening. It is estimated that approximately 320 subjects will need to enter the Acute Phase to provide 240 subjects randomized to the Prevention of Recurrence Phase. Enrollment into the Acute Phase will be discontinued when approximately 240 subjects have been randomized.

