### 9.1. Adverse Events

An AE is any untoward medical occurrence associated with the use of a drug in humans, whether or not considered drug related. An AE can therefore be any unfavorable and unintended sign (including an abnormal laboratory finding), symptom or disease temporally associated with the use of a study drug/study intervention, whether or not related to the study drug/study intervention.

A prior adverse event (PAE) is defined as adverse event whose start date is before the date of the first dose of study treatment. For subjects who didn't take study treatment, all AEs will be identified as PAE. A Summary of the total number of PAE and the number and percentage of subjects with at least one PAE will be provided by SOC and PT based on all screened patients. Besides, a subject listing will be presented for all the prior adverse events.

A TEAE is defined as any event does not present before exposure to study drug or any event already present that worsens in either intensity or frequency after exposure to study drug.

For the purpose of inclusion in TEAE tables, incomplete AE start and end dates will be imputed as follows:

Incomplete onset dates (where UK and UNK indicate unknown or missing day and month respectively):

- UK-*MMM*-*YYYY*: If the month and year are different from the month and year of the date of first dose, assume 01-*MMM*-*YYYY*. If the month and year are the same as the month and year for the date of first dose, and the end date (after any imputation) is on or after the date of first dose, then assume the date of first dose. If the month and year are the same as the date of first dose, and the end date (after any imputation) is prior to the date of first dose, then assume the end date for the start date.
- *DD*-UNK-*YYYY*/UK-UNK-*YYYY*: If the year is different from the year of the date of first dose, assume 01-JAN-*YYYY* of the collected year. If the year is the same as the date of first dose year, and the end date (after any imputation) is on or after the date of first dose, then assume the date of first dose. If the year is the same as the date of first dose, and the end date (after any imputation) is prior to the date of first dose, then assume the end date for the start date.

Incomplete end dates (where UK and UNK indicate unknown or missing day and month respectively):

- UK-MMM-YYYY: Assume the last day of the month;
- DD-UNK-YYYY/UK-UNK-YYYY: Assume 31-DEC-YYYY.

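### The plan leaves open whether a VVC recurrence is an adverse event; any recorded as AEs would attenuate, and if widely recorded could reverse, the pooled any-TEAE comparison in ibrexafungerp's favour

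*Protocol*

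**What the plan says.** Protocol 16.1 lists the disease under study, with its signs and symptoms, among the things that are not AEs, but qualifies this: "unless more severe than expected for the subject's condition or a worsening of the disease being studied". The same section says that an AE can include "An increase in frequency or intensity of a pre-existing episodic event or condition".

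Protocol 14.18.2 sets out how each potential recurrence is listed. Culture-positive episodes are Mycologically Proven, treated episodes resting on KOH and symptoms are Presumed, and empirically treated ones are Suspected. Women with vaginitis from another pathogen "may receive treatment for these conditions as indicated and the vaginitis episode should be listed as AE". Section 14.18.3 asks for the recurrence category as the reason for any antifungal use.

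For the period after Week 24, Protocol 14.22 (repeated in 16.10) says new AEs "will be recorded only if they led to the use of other antifungal medications or topical vaginal treatment". Two further triggers are given there: infection of the vagina by bacteria or parasites, and a judged link to study drug. Protocol 14.11 leaves each site to decide which diary entries become AEs. About 50 centers are expected (10.4).

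SAP 9.1 counts as treatment-emergent "any event already present that worsens in either intensity or frequency after exposure to study drug". It plans an overview of any TEAE by arm and period, and 9.1.1 to 9.1.3 plan tables by system organ class and preferred term, by relationship and by severity. None contains a rule for VVC recurrences. Safety is descriptive only (Protocol 18.7.2).

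**The concern.** Two sites could handle the same episode differently, each with support in the text. Women are randomized at a VSS score of 2 or lower (11.1), and Proven and Presumed Recurrences need 3 or higher (14.18.1). One site may see a worsening of the studied disease and record an AE. Another may see the expected course of recurrent VVC, follow 14.18.2, and record none. After Week 24 the pull towards recording is stronger, because antifungal treatment is part of the definition of all three recurrence categories and is also one of the few stated triggers for recording an AE.

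The events at issue are the components of the primary endpoint, and the trial is designed on the expectation that they are more common on placebo. Recorded as AEs, they would carry part of the efficacy difference into the safety tables, with a predictable sign. As no safety test is planned, the any-TEAE row will be read at face value.

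**Working it through.** **1. The plan's own figure.** Protocol 18.1: "Assuming response rates of 65% and 43% for ibrexafungerp and placebo, respectively; 90% power; and an alpha level of 0.05", from which "approximately 240 subjects randomized at a 1:1 ratio are needed to declare a difference", using Fisher's Exact test. Protocol 18.0: "All statistical tests will be two-sided and interpreted at a 5% significance level". The normal approximation gives 106 per arm (212 in total) uncorrected and 115 per arm (230) with continuity correction. Full enumeration of Fisher's test gives power 0.904 at 114 per arm and 0.909 at 120 per arm. The stated 90% at 240 reproduces, with N rounded up.

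**2. Implied failure to Week 24.** 1 - 0.65 = 0.35 and 1 - 0.43 = 0.57, a gap of 22 points. These are upper bounds on recurrence, because Protocol 18.4 counts a missing TOC as failure. No dropout rate is given. With equal, non-informative dropout d (assumed range 0 to 15%), recurrence is 1 - 0.65/(1 - d) v 1 - 0.43/(1 - d): 27.8% v 52.2% at d = 10%, and 23.5% v 49.4% at d = 15%.

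**3. Formula.** Let a be the true non-VVC TEAE rate, r the recurrence rate, and f the share of recurrences recorded as AEs. Assuming recurrence and other TEAEs are independent, and f is the same in both arms:

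observed any-TEAE = 1 - (1 - a)(1 - f r).

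The documents give no TEAE rates against placebo, so every a below is an assumption.

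**4. Worked case, a = 40% v 30%, no dropout.**
- f = 0: 40.0% v 30.0%, +10.0 points.
- f = 0.25: 1 - 0.60 × 0.9125 = 45.25% v 1 - 0.70 × 0.8575 = 39.975%, +5.3.
- f = 0.5: 1 - 0.60 × 0.825 = 50.5% v 1 - 0.70 × 0.715 = 49.95%, +0.6.
- f = 1: 1 - 0.60 × 0.65 = 61.0% v 1 - 0.70 × 0.43 = 69.9%, -8.9.

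**5. Range.** Difference in points, ibrexafungerp minus placebo, no dropout. The sign changes at f = (a_I - a_P) / [(1 - a_P) × 0.57 - (1 - a_I) × 0.35].

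| Assumed true rates | f = 0 | f = 0.25 | f = 0.5 | f = 1 | Sign changes at f |
|---|---|---|---|---|---|
| 25% v 20% | +5.0 | +0.2 | -4.7 | -14.4 | 0.26 |
| 30% v 20% | +10.0 | +4.7 | -0.5 | -11.1 | 0.47 |
| 40% v 30% | +10.0 | +5.3 | +0.6 | -8.9 | 0.53 |
| 50% v 40% | +10.0 | +5.8 | +1.7 | -6.7 | 0.60 |
| 55% v 40% | +15.0 | +10.4 | +5.8 | -3.4 | 0.81 |
| 70% v 50% | +20.0 | +15.5 | +11.0 | +2.0 | never |

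Dropout of 10 to 15% lowers these thresholds by at most about 0.04. At 40% v 30% and f = 1 the difference becomes -9.9 and -10.5.

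**6. Limit of reversal.** Even at f = 1 the sign flips only if a_I < 1 - (1 - a_P) × 0.43/0.65. For placebo rates of 20, 30, 40 and 50% this means a true excess below 27.1, 23.7, 20.3 and 16.9 points.

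**7. Preferred-term rows.** A term such as diarrhea is counted on its own, so neither f nor r enters and the row is the same at every f.

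**The case against.** The strongest reply is that 14.18.2 is the specific rule and already settles the matter. It lists yeast episodes as recurrences and sends only other vaginitis to the AE page. Entry requires at least three episodes in 12 months, with a VSS score of at least 4 for the current one, so a further episode is the expected course of the disease and may be milder than the qualifying one. The list containing "An increase in frequency or intensity of a pre-existing episodic event or condition" is permissive, and one recurrence is not an increase over three a year. This has weight: the recurrence procedures lean towards exclusion. But they never say that a recurrence is not an AE, and the exception in 16.1 remains open to sites.

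A reader might infer that every recurrence is an AE under 16.1. That is only one reading. Suspected Recurrences need no VSS threshold (the SAP adds treated episodes scoring below 3), so they need show no worsening from Day 1.

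A reader might also infer that 14.22 turns a recurrence into an AE after Week 24. It does not. It filters events that are already AEs, although its choice of trigger invites sites to record recurrences.

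Finally, a reader might infer that a true excess of harm would be hidden. The preferred-term, relationship and severity tables would show VVC as its own term, and the overview has a treatment-related row. A gastrointestinal excess, which is the earlier signal (diarrhea or loose stool 17% v 3% against fluconazole, Protocol 7.1), would stay visible.

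**Conclusion.** The point holds for pooled counts: the any-TEAE row, the system organ class holding VVC, and the by-period overview. The protocol gives no single rule, and the SAP does not repair this. If the planned efficacy difference is real, any leakage to Week 24 favours ibrexafungerp.

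The size depends on how many recurrences are recorded. If a quarter are, an assumed 10-point excess shrinks to about 5 or 6 points and does not reverse. Reversal needs about half or more recorded (0.47 to 0.69 for placebo rates of 20 to 50%), or a true excess of only about 5 points. An excess of 70% v 50% does not reverse even if all are recorded.

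This rests on assumed TEAE rates, on 35% v 57% as design values that include missing data, on independence, and on the same recording share in both arms. The figures apply to Week 24. The documents give no recurrence rate after TOC, so the effect on the follow-up period cannot be sized, and its direction there depends on the benefit persisting.

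**What to change.** State once, in Protocol 16.1 and 14.18, that Mycologically Proven, Presumed and Suspected Recurrences are captured as efficacy outcomes and are not recorded as AEs, unless they meet an SAE criterion or are more severe than expected for the subject's condition. Align 14.22 and 16.10 with that rule.

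In SAP 9.1, keep the full TEAE tables with every reported and serious event. Removing VVC terms from them would also drop serious VVC events from the overview. Add an any-TEAE summary, overall and by period, that excludes VVC recurrences, with any recurrences reported as AEs on a separate line. Identify them by linkage to the recurrence record, because a site may have reported itching or burning instead of VVC.

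The cost is wording in four protocol sections and one SAP section, one extra table and the linkage programming. No new visits, samples or data are needed, and recurrences remain fully reported as efficacy.
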